6.8. Potential Risks and Benefits to Human Subjects

FA is a rare, inherited recessive disorder characterized by progressive degenerative changes, in particular to mitochondria, which lead to morbidity and mortality at a young age. There is currently no approved therapy for this condition. RT001 offers a novel yet specific approach to mitigation of the harmful oxidative attack on lipids of mitochondrial membranes, which has potential benefit if the hypothesis is proven in this and subsequent efficacy studies. RT001 is based on a common, essential dietary sourced fatty acid, LA. The slight modification to the chemical structure of LA, the site-specific replacement of 2 hydrogen atoms with 2 deuterium atoms, does not impact any of the key properties and fate of the lipid, yet remains functionally active against unwanted, pathological oxidative attack. The deuterium presents low risk (see below) in that it is stably incorporated in covalent bonds, and the amount dosed is relatively low. Thus, the risk-benefit profile is thought to be favorable and suggests a future potential benefit of RT001 treatment in this intractable condition.

In models of neurodegenerative diseases, possible triggers such as an aberrant protein (e.g., beta amyloid or synuclein), the low expression of frataxin in FA, chemical or environmental toxins, or redox imbalances, induce a stress in the cell that is first manifested in lipid peroxidation inside mitochondria where several factors combine to make the cells most susceptible. Those factors include: 1) the high concentration of ROS generated by cellular energy generation; 2) the concentrated accumulation of highly susceptible PUFAs in the mitochondrial inner membrane; and 3) inadequate protection by antioxidants due to the hydrophobic nature of the inner membrane that limits antioxidant solubility and diffusion into the susceptible domains. Most important to our mechanism of action is the recognition that the accelerated free radical chain reaction that results from disease amplifies damage massively through an autocatalytic process that propagates recurring damage from a single initiating event. The initiating event is a slow, rate determining step that is self-propagating in its damage to membranes. Stabilizing the bonds most susceptible to oxidation in the initiating event can shut down an entire cascade of accelerating damage in a non-stoichiometric fashion and can provide a new treatment modality for disorders of lipid peroxidation.

RT001 is a site-specific deuterated analogue of LA ethyl ester. LA is designated by the FDA as GRAS with no upper limit set by toxicity. The exposure to LA in the typical Western diet ranges from 5 to 20 g/day. Intralipid® 20%, a product approved by FDA for intravenous (IV) parenteral nutrition, can be administered at doses which provide up to 93 g/day of LA (2.5 g/kg of Intralipid which is up to 2/3 LA). As demonstrated in nonclinical and *in vitro* studies, there were no

demonstrable adverse metabolic effects of deuterating LA. Likewise, the amount of deuterium to be administered at the highest dose proposed for use in this clinical study is approximately four-orders of magnitude lower than the safety threshold described by the International Atomic Energy Agency (IAEA, 2009).

Linoleic acid is the predominant fatty acid in two emulsions approved by the FDA as a source of calories and essential fatty acids. Intralipid 10% (Cutter Pharmaceuticals, IND 17-643) was submitted as an NDA on August 9, 1974. Also, around this time, Liposyn 10% (Abbott Laboratories, IND 18-203) also was filed. These intravenous formulations were developed to provide nutrition to patients who had conditions which precluded effective enteral feeding. Subsequent to these approvals, some changes have been made to the concentration and plant source for the various products, but the component fatty acids have remained consistent.

Intralipid is predominantly soybean oil in concentrations of 10%, 20% and 30%. Egg yolk phospholipids are added in a concentration of about 1.2%. Liposyn includes both soybean and safflower oil in the identical concentrations. The approximate major component fatty acids include linoleic (65%), oleic (20%), palmitic (5%), linolenic (5%), and stearic (5%). Intralipid was approved based on the results of 67 studies conducted before approval. These included 4 studies in 22 human volunteers, and 63 studies in 298 patients. Of the patients included in the studies, 128 were adults, and 170 were pediatric patients (mostly infants). The studies showed that the product was pharmacologically inactive and relatively well-tolerated. Most adverse drug reactions were related to the route of administration rather than to the systemic effects of the product itself. These reactions included: local vein reaction, sepsis, allergic reactions, hyperlipidemia, fever, sleepiness, headache, nausea, vomiting, flushing, hypercoagulability, thrombophlebitis, thrombocytopenia, leukopenia, tachycardia, dyspnea, splenomegaly, and shock.

Post approval, deaths were reported in association with Intralipid use in pre-term infants. This was thought due to fat accumulation in the lungs in these infants. The maximum dose used in pediatric patients was reduced to 3 g/kg/day, and a warning placed on the label for use in pediatric patients.

Deuterated LA and other deuterated PUFAs have been used safely and extensively in biochemistry and nutrition research for several decades to elucidate the metabolic pathways for fatty acid metabolism, cell membrane integrity and prostaglandin synthesis (Brenna, 1997). Single and multiple doses of deuterated PUFAs (up to 10-18 g) have been used in clinical studies without adverse reactions. A wide variety of deuteration positions on LA have been used for those studies, and some, including perdeuterated LA, included deuterium at the C11 position. For example, Emken and colleagues investigated the desaturation of 18:0 and 16:0 and 18:2n-6 and 18:3n-3 elongation/desaturation in four healthy adults, who received oral doses of about 3-3.5 g of d₂-18:2n-6, d₄,-18:3n-3, and d₆-18:n-9 fatty acids (Emken et al., 1990). Salem and colleagues

have safely administered d₅-18:2n-6 and d₅-18:3n-3 doses of 50-10 mg/kg body weight to premature infants and showed that infants as small as 1,980 g and 32 weeks gestation elongate and desaturate both precursors within 24 hours (Salem et al., 1996).

Based on the initial analysis of data from RT001-002, RT001 remains very safe. The maximal tolerated adult dose studied is approximately 9.0 g/d above which steatorrhea/diarrhea may occur. In the initial 28-day study, signs of clinical activity may have been demonstrated. These changes in clinical activity markers were not expected in this 28-day study, but they form the basis for Study RT001-006 where RT001 will be dosed for 11 months.

6.9. Description and Justification for the Dosing Regimens to Be Studied

LA cannot be synthesized by mammals and is an essential component of the human diet. LA is the most common dietary source of polyunsaturated fat for humans and is a source of metabolic energy (9 Calories/g) and longer chain omega-6 fatty acids. LA is also the starting compound for other desaturated and elongated fatty acids that are normal physiological lipid components (e.g., arachidonic acid 20:4n-6), an important fatty acid in membrane phospholipids. Nonclinical studies have shown that RT001 recapitulates LA biochemistry in normal physiological lipid processing.

The amount of deuterium contained in the high dose proposed for the clinical study is below doses commonly used for isotope labeling studies. The dose of RT001 will contribute approximately 80 Calories and is within the range of daily fat intake recommended by the Centers for Disease Control (CDC).

RT001 has been administered in humans at a higher level than the current study proposed dosing regimen and was found to be safe in Study RT001-002. There was one treatment emergent adverse event report characterized as serious – steatorrhea associated with the use of study drug. The event resolved after 6 hours. The subject was hospitalized for overnight observation. The subject had no other symptoms and did not receive specific treatment. Upon questioning, a few other subjects in the high dose cohort also reported occasional diarrhea that was mild and not worrisome. The dose for this study is 8.64 g/d for 30 days followed by 5.76 g/day, which is well below the highest tested dose of 9.0 g/day in Study RT001-002.

7. STUDY OBJECTIVES

This study is designed to evaluate the effect of RT001 in subjects with FRDA:

7.1. Primary endpoint

1. To demonstrate the efficacy of RT001 compared to placebo on the change of MVO2 in patients with FA through change from baseline to 11 months

7.2. Key secondary endpoint

1. To demonstrate the efficacy of RT001 compared to placebo on an overall performance score based on a GST change from baseline to 11 months. The GST will be a combination of three endpoints (timed 1 minute walk test [T1MW], peak workload, and MVO2).

7.3. Secondary endpoints

- 1. To demonstrate the efficacy of RT001 compared to placebo on T1MW with change from baseline to 11 months
- 2. To demonstrate the efficacy of RT001 compared to placebo on the change of peak workload measured by CPET through change from baseline to 11 months

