2. STUDY SYNOPSIS

Sponsor:	Retrotope, Inc. [name]
Title:	A Randomized, Double-Blind, Controlled, Phase 2/3 Study to Assess Efficacy, Long Term Safety and Tolerability of RT001 in Subjects with Friedreich's Ataxia
Protocol No:	RT001-006
Study Drugs:	Active : RT001, 960 mg soft gelatin capsules (9-cis, 12-cis-11,11-D ₂ -linoleic acid ethyl ester [deuterated ethyl linoleate, or D ₂ -LA])
	Placebo: Soft gelatin capsule of USP safflower oil (Placebo or H ₂ -LA)
Study Population:	Friedreich's ataxia (FRDA) patients who meet all entry criteria.
Number of Subjects	The planned enrollment is 60 subjects randomized 1:1 (active: placebo). Randomization will be stratified by Friedreich Ataxia Rating Scale (FARS) Neurological score: ≤45 and >45 Enrollment of patients with age > 25 will be capped at 25 % of the total enrollment
Dosing Schedule	Subjects will receive the content of nine capsules daily (8.64 g total dose) given as 3 capsules three times a day (TID) with meals for the first month of treatment. After this initial loading period, the dose will be reduced to six capsules daily (5.76 g total dose) given as 3 capsules with breakfast, and 3 capsules with dinner for the remainder of the trial, while on study drug. If a subject is unable to tolerate study drug because of adverse events during the initial loading period, the dose may be reduced to six capsules daily (5.76 g total dose) given as 3 capsules with breakfast, and 3 capsules with dinner. If a subject is unable to tolerate study drug because of adverse events after the dose reduction to six capsules daily (5.76 g total dose), the dose may be spread over three meals (2 capsules at breakfast, 2 capsules with lunch, and 2 capsules with dinner). If the subject is still unable to tolerate study drug after spreading it over three meals, the total dose may be reduced by 1-2 capsules/day, preferably by reducing the dose for a meal from 2 to 1 capsule(s) as needed. After 2 weeks of taking a dose of less
	than 6 caps/day, the subject should try to increase the dose to 6 capsules/day given as 2 capsules TID given with meals. If 6 caps/day is not tolerable, the subject can take the drug at the dose of less than 6 caps/day that was tolerable.
Route of Administration:	Oral
Study Centers:	up to 10 study centers
Phase of Development	Phase 2/3

Objectives

Primary endpoints:

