For the primary analysis of peak workload, group sample sizes of 30 and 30 achieve over 99% power to reject the null hypothesis of equal means when the population mean difference is $\mu 1$ - $\mu 2 = 7.5$ - -8.3 = 15.8 with a standard deviation for both groups of 11.1 and with a significance level (alpha) of 0.05 using a two-sided two-sample equal-variance t-test.

Safety Monitoring

The blinded safety and efficacy data will be reviewed by the medical monitor on an ongoing basis. A Data Safety and Monitoring Board (DSMB) will be established to evaluate events according to the DSMB Charter. The safety and efficacy review data will not be made available to the Principal Investigators unless changes need to be made to the protocol for safety reasons.

Table 1: Schedule of Events

Assessments	Study Period	Screening		Study Drug Administration						
	Clinic Visit No.	1	2	Phone Call	3	Phone Call	4	Phone Call	5	End of Treatment Phone Call
	Study Day	Up to 30 Days	Day 1	Days 30,60, 90 (± 7 days)	Day 120 (± 30 days)	Days 150, 180, 210 (± 7 days)	Day 240 (±30 days)	Days 270, 300 (± 7 days)	Day 330 (±30 days)	4 weeks after Day 330 visit (+ 7 days)
Informed Conser	it	X								
Inclusion/Exclus	ion Criteria	X	X							
Demographics/M	ledical History	X	X							
Columbia-Suicid Rating Scale	e Severity	X								
Echocardiogram ^a	ı	X							X	
Serum Pregnancy	/ Test ^b	X								
Cardio-Pulmonai (CPET) ^c	y Exercise Test	X	X		X		X		X	
T1MW and T25I	FW .	X	X		X		X		X	
Physical Exam		X	X		X		X		X	
FARS-Neuro and CGI ^d	l clinician-rated	X^d	X^d		X		X		X	
Speech Measurer	ment Recording	X	X				X		X	
Subject complete Assessment Ques	d Speech stionnaire	X	X				X		X	
FARS ADL, SF3	6, VAS ^e	Xe	Xe		X		X		X	
Subject completed PGI-Cf, Fatigue scale, and Neuro-QoL scales		X^{f}	X ^f	X	X	Х	X	X	X	
Fall Questionnaire		X	X	Xg	X	Xg	X	Xg	X	
Vital Signs (including weight)		X^h	X		X		X		X ^h	
12-Lead ECGi		X	Xi		X		X		X	
Urine Pregnancy	Test ^{b,1}		X		X		X		X	X^{l}
Urinalysis		X							X	
Safety Laborator	y Tests ^{i,j,k}	X	Xi		X		X		X	

Protocol RT001-006: A Randomized, Double-Blind, Controlled, Phase 2/3 Study to Assess Efficacy, Long Term Safety and Tolerability of RT001 in Subjects with Friedreich's Ataxia

Lipid Profile ^{i,k}	X	Xi		X		X		X	
Randomization		X							
In-Clinic Drug Administration		X		X		X		X	
Study Drug Dispensing ^m		X		X		X		X	
Perform Drug Accountability ⁿ				X		X		X	X ⁿ
PK Sampling				X		X		X	
Biomarker Sampling		X		X		X		X	

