Change from baseline (CFB) will be analyzed by comparing the change between treatment groups using a mixed model with repeated measures (MMRM). The MMRM will compare the estimated change from baseline between treatments for the primary endpoint. This analysis will assess whether there is a difference in estimated CFB between active and placebo groups at 11 months.

The primary analysis will use the ITT methodology and an MMRM methodology with a random slope and intercept for each individual. Due to the small sample size the model will be optimized by implementation of two risk scores (baseline and slope) that account for multiple baseline covariates in one variable. The risk scores will be derived from blinded data using the GST change from baseline values and generated using the baseline model covariates (excluding treatment and visit; baseline risk score) or the baseline model covariates*time interactions (slope risk score). The risk scores will be included as covariates in the model.

To calculate the baseline risk score, the GST change score is regressed on the covariates listed below. Individual coefficients for the baseline risk score are multiplied by individual covariate values and summed. A separate slope risk score is calculated for baseline covariates interacting with time.

The MMRM with primary outcome CFB value as the response variable will include the following covariates and fixed effects:

- baseline risk score:
 - baseline score for GST
 - age
- slope risk score:
 - baseline score for GST * time
 - age*time
- Time (continuous)
- Time by treatment interaction (time*treatment)
- baseline score for parameter of interest (if not in GST)
- site pooled by region (random effect)

Model assumptions will be evaluated. If the parametric assumptions are evaluated as inappropriate or violated, rank analogues will be advanced.

All secondary and exploratory endpoints CFB values will be analyzed using the MMRM described above. This analysis will assess whether or not there is a difference in estimated CFB values between treatment group and placebo at the 11-month model estimate using least squares means estimates from the MMRM model.

Speech measurement reporting will be analyzed by a third party vendor. A separate report will be provided.

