14.2. Determination of Sample Size

For the primary analysis of peak workload, group sample sizes of 30 and 30 achieve over 99% power to reject the null hypothesis of equal means when the population mean difference is $\mu 1 - \mu 2 = 7.5 - 8.3 = 15.8$ with a standard deviation for both groups of 11.1 and with a significance level (alpha) of 0.05 using a two-sided two-sample equal-variance t-test.

Subjects who discontinue from the study may be replaced.

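### No testing order links the MVO2, GST, T1MW and peak workload claims, so if each is judged at 0.05 the chance of a false benefit result is about 5.3-7.2% rather than 2.5%

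*Combined protocol and SAP*

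**What the plan says.** Sections 7.1 to 7.3 set out three tiers. MVO2 is the primary endpoint. GST, a combination of T1MW, peak workload and MVO2, is the key secondary: "To demonstrate the efficacy of RT001 compared to placebo on an overall performance score based on a GST change from baseline to 11 months". T1MW and peak workload are the secondaries, and the T1MW objective reads "To demonstrate the efficacy of RT001 compared to placebo on T1MW with change from baseline to 11 months". The peak workload and MVO2 objectives use the same verb.

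Section 14.1 describes a single MMRM with the treatment difference estimated at 11 months, and extends it: "All secondary and exploratory endpoints CFB values will be analyzed using the MMRM described above". It states no significance level and no condition for testing one endpoint after another. The only level in the document is in the sample-size paragraph (synopsis and Section 14.2), "with a significance level (alpha) of 0.05 using a two-sided two-sample equal-variance t-test", and that paragraph calls peak workload the primary analysis.

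Section 14.1 defers full detail to a separate SAP, to be finalised before unblinding. Section 14.3 discusses alpha only for the two optional interim analyses, and allows the sponsor to change the order of the leading endpoints after either of them.

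**The concern.** Primary, key secondary and secondary are labels of importance. They do not say whether a GST, T1MW or peak workload result may support an efficacy claim when MVO2 has missed. Four endpoints share one verb, one model and one available level, so nothing in the text prevents a nominal p<0.05 on a lower endpoint from being reported as a demonstration.

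The endpoints are also closely related. GST contains MVO2, and two of its three components come from the same exercise test, so a chance imbalance in one tends to appear in the others. This lowers the overall error rate below that of four independent tests, but it also means that a false positive may come with apparent support from its neighbours.

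The MVO2 test itself is not at stake. What is at stake is the standing of the three further claims, above all in a trial that misses on MVO2.

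**Working it through.** **The plan's own figure.** The plan states "group sample sizes of 30 and 30 achieve over 99% power to reject the null hypothesis of equal means", for a difference of "15.8 with a standard deviation for both groups of 11.1". The noncentrality is 15.8 / (11.1 × √(2/30)) = 15.8 / 2.866 = 5.51. With 58 degrees of freedom, two-sided 0.05, the power is 0.9997. The stated figure reproduces. It concerns peak workload alone and says nothing about the joint behaviour of four tests.

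**Inputs.** From the documents: four endpoints (Sections 7.1-7.3), GST built from the other three (Section 7.2), a common contrast (Section 14.1), two-sided 0.05 (Section 14.2). Assumed, because the documents give no figures: an MVO2-peak workload correlation of 0.5 to 0.9, a correlation of T1MW with each exercise-test measure of 0.2 to 0.6, and GST as the equal-weight mean of the three standardised components.

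**Method.** Draw three correlated standard normal statistics under no effect, form GST as their standardised sum, (z₁+z₂+z₃) / √(sum of all entries of the correlation matrix), and test each of the four against ±1.96. There were 2,000,000 draws per setting.

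| Correlations (MVO2-peak workload, T1MW-exercise test) | Any of four significant, either direction | Any of four falsely favouring RT001 | MVO2 misses, another falsely favours RT001 |
|---|---|---|---|
| 0.9, 0.6 | 10.6% | 5.3% | 2.8% |
| 0.8, 0.5 | 11.8% | 5.9% | 3.4% |
| 0.7, 0.3 | 13.1% | 6.6% | 4.1% |
| 0.6, 0.4 | 13.1% | 6.6% | 4.1% |
| 0.5, 0.2 | 14.3% | 7.2% | 4.7% |
| Nominal, MVO2 alone | 5% | 2.5% | - |

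The last column follows from the one before it by removing the primary's own share: 5.3 − 2.5 = 2.8 and 7.2 − 2.5 = 4.7. The remaining corners of the assumed ranges, (0.9, 0.2) and (0.5, 0.6), give about 12% in the either-direction column, inside the range shown.

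**Sensitivity.** With one common correlation among the three components, the either-direction rate is 16.1% at 0, 14.4% at 0.3, 13.0% at 0.5, 11.1% at 0.7 and 8.4% at 0.9. The matching rates favouring RT001 are 8.2%, 7.2%, 6.5%, 5.5% and 4.2%. Four independent tests would give 1 − 0.95⁴ = 18.5%, which cannot apply here because GST is made from the other three.

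**After the fix.** In a fixed sequence, no endpoint can be claimed unless MVO2 is significant first. Under no effect, the chance of any false positive is therefore the MVO2 rate, 5.0% (2.5% in favour of RT001), at every correlation.

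**The case against.** The strongest reply is that this is a protocol and not the full analysis plan. Section 14.1 promises a complete description of methods in a SAP, and a testing hierarchy is a normal item there. That stands: the supportable statement is that the reviewed text has no rule, not that the trial will have none. But Section 14.1 already specifies the model, the covariates and the responder analyses, so a testing order would not be out of place in it.

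Second, the wording is weak evidence of a confirmatory family. Section 7.4 introduces five listed exploratory measures with the same verb, so it may be template language. No section defines success for a secondary endpoint, and the 0.05 appears only in a power calculation. A reader might infer that the plan licenses a secondary claim after MVO2 fails. The documents do not say so; they simply do not rule it out. The tiers, and the talk in Section 14.3 of re-ordering, suggest that some order was intended.

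Third, a reader might conclude that the chance of a false efficacy claim is 11-14% instead of 5%. That does not hold as stated. The count includes results significantly favouring placebo, which cannot demonstrate efficacy of RT001, and it depends on correlations and GST weights that the documents do not give. The benefit-only rates are about half as large.

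What survives is that no rule is written, and that across the whole range examined the rate exceeds the nominal one.

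**Conclusion.** The point holds as a gap that should be closed before unblinding. It is not a flaw in the primary test, which keeps its 5%.

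If each of the four endpoints is judged at two-sided 0.05, the chance under no effect of at least one result falsely favouring RT001 is about 5.3-7.2% against 2.5%, or 10.6-14.3% against 5% counting both directions. The chance that MVO2 misses and another endpoint falsely favours RT001 is about 2.8-4.7%. The size is conditional on the assumed correlations and the equal-weight GST. The direction is not: even at a common correlation of 0.9 the two-sided rate is about 8%, and at 0 it is about 16%.

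Two features make a written order more necessary than usual. The sample-size text calls peak workload the primary analysis, whereas Section 7.1 names MVO2 and Section 7.3 makes peak workload a secondary. And Section 14.3 lets the order change after interim results, in terms of CPET (without saying which measure) and mFARS, which Section 7.4 lists as exploratory.

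**What to change.** Add to Section 14.1, and repeat in the SAP: *MVO2, GST, T1MW and peak workload are tested in this order, each at two-sided 0.05. Testing stops at the first non-significant result. Endpoints after that point, and all exploratory endpoints, are reported with nominal p-values and without a claim of demonstrated efficacy.*

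Two further changes are needed for this to work:

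- Correct the sample-size text in the synopsis and Section 14.2 so that the endpoint it calls primary agrees with Sections 7.1-7.3.
- State in Section 14.3 that the order will not be changed on the basis of unblinded interim futility results. The second interim reports the results of futility analyses on about half the subjects. Even if the sponsor never sees treatment assignments, moving the better-looking endpoint to the front selects on the treatment comparison, and the 5% control then no longer holds.

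The cost is one paragraph and two corrections. MVO2 loses no power. The real price is that no formal claim on GST, T1MW or peak workload is possible if MVO2 misses, and that peak workload, the only endpoint with a power calculation, comes last, behind three endpoints with no stated power. The sponsor should accept that openly when fixing the order.
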